9.3.1 Exposure of Interest

Doses of MenACWY-CRM administered at a KPSC facility are considered as exposures of interest in children 2-23 months of age who are KPSC members. The exposure of interest is MenACWY-CRM vaccine given as part of routine clinical care in all medical centers in KPSC. This study is strictly observational. MenACWY-CRM will be the only meningococcal vaccine used in children 2-23 months of age to prevent *N. meningitidis* serogroup A, C, W135 and Y caused meningococcal disease in KPSC. While HCPs are

advised to follow ACIP immunization recommendations, decisions regarding vaccinations and vaccination schedule will be determined by the HCP and caregivers. The MenACWY-CRM vaccination recommendation will be implemented at all KPSC medical centers.

No special labeling will be required for the MenACWY-CRM vaccine used in this study. Other vaccines may be co-administered as consistent with clinical practice.

According to the ACIP recommendation, MenACWY-CRM is recommended for infants and toddlers 2-23 months of age with high risk of meningococcal disease. The recommended meningococcal vaccination schedules for these high risk populations are as follows: [10]

- Children with anatomic or functional asplenia (including sickle cell disease):
 1. For children younger than 19 months of age, administer a 4-dose infant series of MenHibrix or MENVEO at 2, 4, 6, and 12 through 15 months of age.
 2. For children aged 19 through 23 months who have not completed a series of MenHibrix or MENVEO, administer 2 primary doses of MENVEO at least 3 months apart.
- Children with persistent complement component deficiency:
 1. For children younger than 19 months of age, administer a 4-dose infant series of either MenHibrix or MENVEO at 2, 4, 6, and 12 through 15 months of age.
 2. For children 7 through 23 months who have not initiated vaccination, two options exist depending on age and vaccine brand:
 - a. For children who initiate vaccination with MENVEO at 7 months through 23 months of age, a 2-dose series should be administered with the second dose after 12 months of age and at least 3 months after the first dose.
 - b. For children who initiate vaccination with Menactra at 9 months through 23 months of age, a 2-dose series of Menactra should be administered at least 3 months apart.

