9.3.3 Other Variables

- Baseline characteristics: these data will be extracted from patients' medical records.
 - Date of birth, expressed as age at vaccination
 - Gender
- Underlying condition of the MenACWY-CRM vaccine indication (i.e., persistent complement component deficiencies, asplenia or other), if available.
- Vaccination history
 - Concomitant vaccinations (specify)
 - History of other vaccinations (specify)
 - Vaccinations occurring during the observation period (specify)

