9.4 Data Sources

The study will be conducted using the KPSC Oracle Research Data Warehouse (RDW) which supports external and internal research projects conducted in the Department of Research & Evaluation, KPSC as well as patient care management programs. The data warehouse is an integrated and comprehensive resource. It contains information as far back as 1980, including records related to membership, benefits, utilization, pharmacy, vital signs, laboratory, vaccines, geocoding, mortality, and procedures.

Medical events will be searched in the electronic medical record (EMR). All care provided at KPSC is recorded using the EMR. All details of a patient encounter, including diagnoses, procedures, and physician's notes, are entered into the EMR at the point of care. All vaccinations are entered into the EMR when they are given, with vaccine, dose, manufacturer, and lot number entered at the time of vaccination.

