9.4.3 Operational Variable(s) Definition

To describe medical events, baseline characteristics, including date of birth, gender, date of diagnosis, and underlying condition will be extracted from medical records. Vaccination history will be extracted from immunization records.

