3.2 Sample Size and Power Considerations

As the study is descriptive in nature, there is no hypothesis testing and therefore no requirement for a given sample size or power. The sample size will be determined by the total number of children aged 2-23 months vaccinated in KPSC during a three-year period.

Approximately 245,000 infants and toddlers aged 2-23 months were enrolled in the KPSC health plan in the period from 2011 to 2013. Among this population, there were around 60 children aged 2-23 months old with high risk medical conditions. It is estimated that the number of infants with high risk conditions would likely fall between 60-100 in the study period.

The following table provides the width of the confidence intervals for the incidence rate estimates for different sample sizes and observed event rates. It assumes that each individual recipient will provide, on average, one person-year of follow-up among all doses.

Table: Expected confidence intervals by event rate and study sample size.

Event rate per 100 person-years	Number of vaccinated subjects		
	N=50	N=100	N=150
0.1	0.0-7.6	0.0-3.9	0.0-2.7
1.0	0.0-9.4	0.0-5.6	0.1-4.3
10	3.3-23.3	4.8-18.4	5.6-16.5
100	74.2-131.8	81.4-121.6	84.6-117.3

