3.3.3 Outcomes

Outcomes include medical events that require ED visits or hospitalizations in children 2-23 months of age following any dose of MenACWY-CRM vaccination. Medical events occurring in ED and inpatient settings within 6 months following a MenACWY-CRM vaccination will be searched in the EMR. Evidence of the same pre-existing medical event (based on ICD diagnosis code) will be searched for in all care settings (inpatient, outpatient, or ED) prior to the first dose of MenACWY-CRM vaccination.

Events with a history of the same diagnosis prior to the first dose of MenACWY-CRM vaccination will be excluded as a pre-existing condition. The medical records prior to the first dose of MenACWY-CRM will be searched for the same diagnosis code. As there will be a transition from International Classification of Diseases, Ninth Revision (ICD-9) to Tenth Revision (ICD-10) coding, in the event that the diagnosis following a MenACWY-CRM vaccination is coded using ICD-10, both the same ICD-10 code and an equivalent ICD-9 diagnosis code will be searched in the period prior to the first dose.

If a study subject is first seen in the ED and subsequently transferred to the hospital, this will be treated as a single event.

For each identified ED or inpatient visit the following information will be collected:

- Diagnosis of medical events
- Date of diagnosis: the date of the documented code after any dose of MenACWY-CRM vaccination is considered the date of diagnosis. The date of diagnosis is expressed as the number of days following the 1st, 2nd, 3rd, or 4th dose of MenACWY-CRM vaccination.
- Health care setting: hospitalization or ED or both
- First occurrence vs. recurrence of the diagnosis

One subject can experience multiple different events. In the specific situation where an eligible child received multiple doses during the observation period and the event occurred after the administration of a later dose, the timing of the event is calculated from the date of administration of the most recent dose. In the case of a recurrence of the same condition, the initial diagnosis and the recurrent diagnosis will each be separately described relative to the most recent dose.

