5.1 Identification and review of events

Medical events occurring in ED and inpatient settings within 6 months following a MenACWY-CRM vaccination will be searched in the EMR.

Medical events will be characterized two ways: by encounter (hospitalization only, ED only, or both ED and hospitalization) and by diagnosis (see Appendix A, Table Shell 4 for details). The analysis allows for any recurrent events (i.e. different episodes of the same diagnosis) to be counted independently.

For characterization by encounter (Table 4a), all dates used for analysis will be the date of the ED encounter or hospital admission. Encounters will be considered pre-existing if all diagnoses made during the encounter are present in the medical record prior to the first dose of vaccine. Upon chart review by the study physician co-investigator, an encounter will be refuted if it is found to not be a true ED or hospital encounter. Each encounter will be reported as a single event, regardless of the number of diagnoses made during the encounter.

For characterization by diagnosis (Table 4b), all dates used for analysis will be the first date that the diagnosis is recorded in the EMR in any medical setting. A diagnosis will be excluded as pre-existing if the same ICD diagnosis code appears in any medical setting prior to the first dose of MenACWY-CRM vaccination. A diagnosis will be considered refuted if, upon chart review by the study physician co-investigator, there is no evidence of the diagnosis in the medical record. Multiple diagnoses associated with the same episode will be identified, but only the first diagnosis date (in any setting) will be counted in the analysis of each episode. Subsequent diagnoses for the same episode will be marked in Table 4b as “Diagnosis is continuation of an ongoing episode.” An episode will be considered as ended when there is symptom resolution as determined by chart review (e.g., symptoms stated to have resolved or the diagnosis/symptoms have been absent from the medical record before they are mentioned again). In the case of recurrent events, the date used will be the date of the first diagnosis in the medical record following resolution of the prior episode. Recurrent events will be marked in Table 4b as “Diagnosis is a recurrence”. Each diagnosis will be described independently. It is possible that different diagnoses from the same inpatient or ED encounter could have different diagnosis

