Appendix B: Underlying condition of vaccine indication

Vaccine recipients will be determined to have the following underlying conditions for vaccination if the associated diagnosis codes are present in the medical record six months prior to index vaccination, including the date of index vaccination.

1. Asplenia

Functional - Hemoglobinopathies (primarily sickle cell [SS or SC] disease)

ICD-9 Codes:

Diagnosis	ICD-9 Diagnostic Code
Sickle cell disease unspecified	282.60
HB-SS disease with crisis	282.62
Sickle cell thalassemia without crisis	282.41
Sickle cell/HB-C disease without crisis	282.63
Sickle cell/HB-C disease with crisis	282.64
Other sickle cell disease without crisis	282.68
Other sickle cell disease with crisis	282.69
Sickle cell thalassemia with crisis	282.42

ICD-10 Codes:

Diagnosis	ICD-10 Diagnostic Code
Sickle cell disease without crisis	D57.1
HB-SS disease with crisis, unspecified	D57.00
Sickle cell thalassemia without crisis	D57.40
Sickle cell/HB-C disease without crisis	D57.20
Sickle cell/HB-C disease with crisis, unspecified	D57.219
Other sickle cell disorders without crisis	D57.80

Other sickle cell disease with crisis, unspecified	D57.819
Sickle cell thalassemia with crisis, unspecified	D57.419
Hyposplenism	D73.0

Anatomic Asplenia

ICD-9 Codes:

Diagnosis	ICD-9 Diagnostic Code
Anomalies of spleen congenital	759.0

ICD-10 Codes:

Diagnosis	ICD-10 Diagnostic Code
Asplenia (congenital)	Q89.01
Congenital malformations of spleen	Q89.09
Acquired asplenia	Z90.81

2. Persistent Complement Component Deficiencies

ICD-9 Codes:

Diagnosis	ICD-9 Diagnostic Code
Other specified disorders involving the immune mechanism	279.8

ICD-10 Codes:

Diagnosis	ICD-10 Diagnostic Code
-----------	------------------------

Defects in the complement system	D84.1
----------------------------------	-------

Table 1: Study population selection

Population	Total (n)
Total number of persons within the KPSC cohort	
Total number of children 2-23 months old in the KPSC cohort	
Total MenACWY-CRM vaccine recipients among age 2-23 months	

Date tables created:

Period captured in the tables:

Report integrates the tables:

Table 2: Baseline Characteristics of MenACWY-CRM Recipients 2 to 23 Months of Age

Characteristic	Total	Number of doses received			
		One	Two	Three	Four
Age at first vaccination (months)	mean (sd) median Q1, Q3 (min - max)				
Age 2-6 months at first vaccination	n (%)				
Age 7-23 months at first vaccination	n (%)				
Gender					
Male	n (%)				

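### SAP Appendix B's six-month look-back can place a child with a lasting, already recorded condition under 'Unknown' indication in Table 2

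*SAP*

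**What the plan says.** SAP v2.0 section 4.2 describes recipients by underlying condition and refers to Appendix B for the definition. Appendix B lists ICD-9 and ICD-10 codes for asplenia (functional, mainly sickle cell disease, and anatomic) and for persistent complement component deficiency. It counts a child as having the condition "if the associated diagnosis codes are present in the medical record six months prior to index vaccination, including the date of index vaccination". Draft v1.2 has the same rule. In Table 2, a child without a qualifying code can only go in the row 'Unknown'. Table 6 has the column 'Other or Unknown'.

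The protocol defines the same variable without a time window. Section 9.3.3 lists "Underlying condition of the MenACWY-CRM vaccine indication (i.e., persistent complement component deficiencies, asplenia or other), if available", and section 9.4.3 says that "baseline characteristics, including date of birth, gender, date of diagnosis, and underlying condition will be extracted from medical records". On the data source, section 9.4 says: "It contains information as far back as 1980, including records related to membership, benefits, utilization".

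For pre-existing diagnoses the SAP uses an open-ended look-back. Section 5.1 excludes a diagnosis if "the same ICD diagnosis code appears in any medical setting prior to the first dose of MenACWY-CRM vaccination". Section 3.3.3 adds that, for an event coded in ICD-10, "both the same ICD-10 code and an equivalent ICD-9 diagnosis code will be searched in the period prior to the first dose".

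First doses after six months of age are foreseen. The schedule cited in protocol section 9.3.1 for complement deficiency includes the clause "For children who initiate vaccination with MENVEO at 7 months through 23 months of age", and Table 2 has a row for first vaccination at 7-23 months.

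**The concern.** The conditions in Appendix B do not lapse. A sickle cell or congenital asplenia code entered eight months before the index dose still describes the child on the day of vaccination. The window discards that information, and the SAP gives no reason for doing so.

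At stake is the description of why these children were vaccinated. In this age range the vaccine is recommended only for children at increased risk, so indication is a main descriptor of a small cohort. The error runs one way: named indications are undercounted and 'Unknown' is overcounted. A reader of Table 2 could take a child with a documented condition for one vaccinated for travel, for an outbreak or for no recorded reason.

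**Working it through.** The plan states no figure for this point, so there is none to reproduce. The check compares the rules and then works out which part of the record the window leaves out.

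**1. The two look-backs applied to one child.** Suppose a listed sickle cell code is recorded at 3 months of age and not again up to and including an index dose at 12 months.
- Pre-existing rule (SAP 5.1): the code precedes the first dose, so a later emergency or inpatient diagnosis with that code is excluded as pre-existing.
- Indication rule (Appendix B): the window runs from 6 to 12 months of age, so the code does not count and Table 2 shows 'Unknown'.

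The same record is used as evidence in one place and disregarded in the other.

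**2. Record left outside the window.** Assume records from birth, and let A be exact age in months at the index dose. Months ignored = max(0, A - 6), and the share ignored is that number divided by A.

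| A | Months ignored | Share of record |
|---|---|---|
| 6 or less | 0 | 0% |
| 7 | 1 | 14% |
| 12 | 6 | 50% |
| 15 | 9 | 60% |
| 19 | 13 | 68% |
| 23 | 17 | 74% |
| just under 24 | nearly 18 | nearly 75% |

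Age here is exact. A child of six completed months can be almost seven months old, so a child in Table 2's 2-6 month row can lose up to nearly one month. A child in the 23-month category can be almost 24 months old, so the longest ignored stretch is nearly 18 months. A child who joined the health plan after birth has less record to lose.

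**3. Effect of one affected child.** The SAP's precision table (section 3.2) uses N = 50, 100 and 150.
- 1/50 = 2.0 percentage points
- 1/100 = 1.0 percentage point
- 1/150 = 0.7 percentage points

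Section 3.2 also expects that "the number of infants with high risk conditions would likely fall between 60-100 in the study period". If all of them are vaccinated, one child is 1/100 = 1.0% to 1/60 = 1.7% of that group.

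**4. Where the variable is used.** Inclusion depends on age, membership and vaccination. Tables 4 and 5 are laid out by encounter type or diagnosis, number of doses, setting and recurrence. None of these uses indication. That leaves Table 2, which section 4.2 ties to Appendix B, and Table 6. Section 5.3, which governs Table 6, does not cite Appendix B, but the Table 6 column heading repeats the Appendix B title. Table 6 covers only diagnoses or groupings with at least five confirmed episodes.

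**The case against.** **The consequence is small.** The objective is to describe emergency and inpatient events, and none of the event counts or rates depends on this variable. A child is missed only if a lasting condition goes uncoded in every setting for six months and also on the index date. The documents give no reason to think that is common. This stands, and it sets the grade at minor. It does not defend a rule that discards a valid recorded diagnosis.

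**Six months may be a deliberate baseline.** Table 2 also reports vaccinations in the six months before the index dose, the full look-back for pre-existing diagnoses has a different purpose, and the protocol's silence leaves the window to the SAP. So this is not a contradiction between the documents. But recency matters for a prior vaccination and not for a persistent condition, and no reason for the limit is given.

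**The wording is loose.** The phrase could be meant less strictly, but the inclusion of the index date points to a six-month window. If the whole prior record was intended, the text should say so.

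**Table 6 may draw on chart review.** Section 5.3 says that events are reviewed and summarised, and Table 6 has an 'Other' category that the Appendix B codes cannot produce. This stands in part: the effect on Table 6 is likely but not settled.

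**A longer look-back may add false matches.** Code 279.8 has a broad immune-disorder label, and 759.0 and Q89.09 cover spleen anomalies more widely than asplenia. This stands as a small downside of the change.

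**Conclusion.** The point holds and is minor. As written, Appendix B reports a child as 'Unknown' in Table 2 if the child is older than six months at the index dose and has a listed code recorded only before the window. Table 6 probably follows. How many children this affects cannot be derived, because the documents give no coding frequency and no planned number of vaccinees. It may be none.

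Three stronger readings are tempting and are not supported.
- A reader might take the shares of 14% to nearly 75% as misclassification rates. They are shares of calendar time outside the window, and they rest on the assumption of records from birth.
- A reader might infer that the safety results are biased. Inclusion, event counts, person-time and rates do not use this variable.
- A reader might infer a further undercount because D73.0 and Z90.81 have no evident partner in the ICD-9 lists. The documents contain no crosswalk between the two code systems, so they do not show that any code was left out.

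**What to change.** In Appendix B, replace the six-month window with any time in the medical record up to and including the date of index vaccination. If six months was intended, give the reason instead. In section 5.3 or the Table 6 footnotes, state that Table 6 uses the same classification.

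Add a Table 2 footnote with the number of children classified only from codes older than six months. This shows what the longer look-back adds, including any extra matches on 279.8, 759.0 or Q89.09. It should follow the existing rule that suppresses counts of 1 or 2, so a very small number would be masked.

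The cost is one change to a date window, one cross-reference and one footnote. No new data source is needed, because records before the first dose are already searched for pre-existing diagnoses. 'Unknown' will still hold travel and outbreak recipients, since Table 2 has no row for them.

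### SAP Appendix B's ICD-9 and ICD-10 lists are not equivalent, so some children fall in or out of the asplenia or complement-deficiency group according to the coding system alone

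*SAP*

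**What the plan says.** SAP v2.0 Appendix B classes a recipient as having an underlying condition "if the associated diagnosis codes are present in the medical record six months prior to index vaccination, including the date of index vaccination". It then prints separate ICD-9 and ICD-10 lists for functional asplenia, anatomic asplenia and persistent complement deficiency.

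- **Functional asplenia.** The ICD-9 list gives "Sickle cell disease unspecified" (282.60) and "HB-SS disease with crisis" (282.62), plus rows with and without crisis for thalassemia, HB-C and other sickle disease. The ICD-10 list has the matching rows, a general row for sickle cell disease with no crisis (D57.1), and "Hyposplenism" (D73.0).
- **Anatomic asplenia.** ICD-9 has one row, for congenital anomalies of the spleen (759.0). ICD-10 has two congenital rows (Q89.01, Q89.09) and "Acquired asplenia" (Z90.81).
- **Complement deficiency.** ICD-9 has 279.8, "Other specified disorders involving the immune mechanism". ICD-10 has D84.1, "Defects in the complement system".

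The resulting category is reported in Table 2, where the remaining row is Unknown, and in Table 6, where the remaining column pools Other with Unknown.

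**The concern.** The vaccine is recommended at this age for high-risk children, and underlying condition is the plan's only descriptor of why a child was high-risk. The plan expects the coding system to change during the study. If the two lists describe different conditions, a child's category depends partly on which system was in use at vaccination.

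Nothing else in the plan repairs this. The search for an equivalent ICD-9 code (SAP 3.3.3) and the caveat about imperfect mapping (SAP 6.2) concern diagnoses that pre-date the first dose and are used to exclude outcome events. Physician review (SAP 3.1 and 5.1) is directed at encounters and outcome diagnoses, not at the vaccine indication. No sensitivity analysis is planned (SAP 5.4).

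The numbers are small: SAP 3.2 expects 60 to 100 high-risk children, and Table 2 suppresses counts of 1 or 2. A few children in the wrong row can change that row or blank it.

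**Working it through.** The plan states no figure on this point, so the check is a comparison of the Appendix B lists by their printed labels. No code book is needed for it.

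**Step 1: count and pair the rows.** ICD-9: 8 functional + 1 anatomic + 1 complement = 10 rows. ICD-10: 9 functional + 3 anatomic + 1 complement = 13 rows. Seven sickle-cell rows pair by label: HB-SS with crisis, and thalassemia, HB-C and other sickle disease each with and without crisis (1 + 3 × 2 = 7). The congenital spleen rows also cover similar ground: 759.0 against Q89.01 and Q89.09.

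**Step 2: follow the rule for the rows that do not pair.** This assumes the child carries no other listed code in the six-month window.

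| Child's condition | ICD-9 only | ICD-10 only |
|---|---|---|
| Hyposplenism | no row: Unknown | D73.0: Asplenia |
| Acquired asplenia | no row (759.0 is congenital): Unknown | Z90.81: Asplenia |
| Non-complement disorder coded 279.8 in ICD-9 | 279.8: Complement deficiency | not D84.1: Unknown |
| HB-SS without crisis | Asplenia if coded 282.60 or as a crisis, otherwise Unknown | D57.1: Asplenia |

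The first three rows are the firmest. The fourth depends on coding habit.

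**Step 3: confirm that both lists will be used.** SAP 3.1 sets the index window as 1 July 2014 to 30 June 2017, which is 1,096 days. The documents give no switch date, so I take a range of assumed dates and a look-back of 183 days. Index dates before the switch have an ICD-9-only look-back, the next 183 days straddle both systems, and the rest are ICD-10 only.

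- Switch on 1 January 2015: 184/1,096 = 16.8% ICD-9 only; 183/1,096 = 16.7% straddle; 729/1,096 = 66.5% ICD-10 only.
- Switch on 1 July 2016: 731/1,096 = 66.7% ICD-9 only; 16.7% straddle; 182/1,096 = 16.6% ICD-10 only.

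With uniform accrual (also assumed), about 10 to 40 of 60 children, or 17 to 67 of 100, would be classified on the ICD-9 list alone. These are children exposed to that list, not children misclassified. Most may carry codes that pair.

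**Step 4: trace where the category is used.** It appears in Table 2 and Table 6. It is not an inclusion criterion (Protocol 9.2.3), does not enter the event counts or rates (SAP 5.2), and is not a stratum (SAP section 8).

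**The case against.** The case on the other side is substantial.

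**HB-SS is the softest element.** One listed code is enough, and 282.60 may well be present for a child with HB-SS disease. This stands, and the point is limited accordingly. The jump in numbering from 282.60 to 282.62 proves nothing by itself, since the same list also jumps from 282.64 to 282.68. What does show in the labels is that HB-SS is the only subtype without a row for no crisis.

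**279.8 may be the nearest ICD-9 code available.** The documents do not say whether a narrower one existed. Even if none did, the label still admits disorders that are not complement deficiencies, so confirmation in the record is needed.

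**The consequence is descriptive only.** Underlying condition is reported only where available. Travel and outbreak indications have no Appendix B codes, so Unknown is already a mixed group. Table 6 covers only diagnoses with at least five confirmed episodes. All of this stands and limits the weight of the point, but it does not make the two lists agree.

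A reader might also infer more than the documents support:

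- That a child could move between asplenia and complement deficiency. No row does this; the moves are between each of those groups and Unknown.
- That the indication mix would appear to shift over the study. No planned output shows it by calendar time or coding era; Figure 1 shows vaccinations by month only.
- That Q89.09 is a further mismatch. It reproduces the breadth of 759.0 and makes the two systems more alike.
- That the ICD-10 crisis rows are incomplete because all four are labelled unspecified. That needs a code book, so it is something to check, not a finding.

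**Conclusion.** The point holds in a limited form. Followed as written, Appendix B classifies hyposplenism, acquired asplenia and non-complement disorders coded 279.8 differently in the two coding systems, and may do so for HB-SS without crisis. This rests on the printed labels and on the child having no other listed code in the window.

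The damage is confined to the underlying-condition rows of Table 2 and columns of Table 6. It would be wrong to infer that eligibility, event frequencies or rates are affected, or to read the share of children classified under ICD-9 as an error rate. The documents give no count for any unmatched condition, so the number misclassified cannot be computed. The correction is worth making because it is cheap and, in a group this small, a few children matter to those cells.

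**What to change.** Amend Appendix B so that the two lists correspond condition by condition, checked against the ICD-9 and ICD-10 code books:

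- Add ICD-9 counterparts for hyposplenism, acquired asplenia and HB-SS without crisis.
- Check whether the ICD-10 crisis rows labelled unspecified are complete, and extend them if not.
- Assign complement deficiency from 279.8 only when the electronic record names a complement deficiency; otherwise class the child as Unknown, unless another listed code applies.

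The cost is one appendix edit, a matching change to the code list in the program, and a record look-up for the few children carrying 279.8. No other analysis changes.
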